Another treatment option for patients with advanced PD is Continuous subcutaneous Apomorphine Infusion (CAI). In the Netherlands CAI is used in a smaller number of patients. CAI is not included in this research protocol, because at start of this trial, the evidence for effectiveness of CAI was of poor quality. Besides, CAI is slightly more expensive than DBS. A study that directly compares all three treatments is not feasible because of the large sample size needed.

Both treatment with DBS and CLI is expensive. We estimate that DBS equipment and batteries cost €10,000 per patient/year and CLI equipment and infusion solutions cost

Version 7: 23-10-2019 10 of 48

€45,000 per patient/year. In addition, patients need surgery and they frequently visit the clinic. In a recent Spanish study the mean cumulative 5-year cost per patient (including the surgery) was estimated € 88,014 for DBS and € 233,986 for CLI. [6]

Several level I studies have shown that DBS is efficacious for the treatment of PD motor symptoms: it reduces dyskinesias and motor fluctuations.[7] CLI reduces off-time and is effective for the treatment of motor fluctuations and dyskinesias as was shown in a few small and one larger level I trial. Both therapies significantly improve quality of life.[7-13] No head-to-head comparison of DBS and CLI has been performed, but when comparing individual studies, the effects on quality of life are similar.[8, 13] Little is known about comparative adverse-effects profiles of the therapies. One retrospective study suggests a higher rate of complications in CLI.[14]

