4.4 Sample size calculation

RCT

The primary objective of the study is to realize an efficient allocation of resources to the available treatment options in advanced PD. For this, primarily an economic evaluation will be carried out and the sample size has been calculated accordingly. Society's willingness-to-pay (WTP) per Quality Adjusted Life Year (QALY) may be indicative of whether or not CLI is affordable compared to DBS. The Dutch Raad voor de Volksgezondheid (RvZ) reported a value of €80,000 per additional QALY in 2006 as a potential upper limit of affordability. Explicitly, the figure is reported by the RvZ as a potential, but also unofficial limit: it should

Version 7: 23-10-2019 16 of 48

not be taken as a definite one. Other arguments based on patient preference or access to health care should be taken into account as well. Considering that CLI may be a less invasive intervention and access to health care is easier to facilitate when two interventions can be provided, a more lenient upper limit for the extra societal costs per additional QALY may be appropriate here. We propose a sample size calculation based on a WTP per additional QALY of €120,000 (50% above the RvZ figure). Based on the net health benefit formula suggesting that differences in QALYs between the interventions should be larger than the difference in costs (i.e., €34,174 a year) divided by the maximum WTP (i.e., €120,000 per QALY) in order for one intervention to be accepted as more efficient than another intervention, CLI treatment should at least outperform DBS treatment by 0.2847 QALY per year. Based on literature data with comparable costs estimates, [6] we anticipate standard deviations (SD) for QALYs up to 0.35 and for total costs up to €10,000 (factoring in a 12-month follow-up and non-responders).

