To achieve 80% power and given a two-sided significance level of 0.05, up to 26 patients per group (or 52 in total) are needed to detect a difference of at least 0.2847 QALY for WTP-values up to €120,000 and a worst case scenario of zero correlation between costs and clinical effect, using a two-group t-test. Accounting for a possible dropout of 20%, we will randomize 66 patients (33 per group). With this sample size and given the same test conditions (power, type-I error rate, test chosen, drop-out rate) we are also able to detect a difference in mean PDQ-39 scores between both groups of 11.9, assuming an expected mean score of 32 in the DBS group and a standard deviation of 15.

Motivation for standard deviations for QALY

Literature data [8-10] show that the standard deviation for PDQ-39 scores from operated PD patients equals 15 points and that a 4 to 5 points difference is associated with a QALY difference of approximately 0.1,[16] suggesting a standard deviation for QALYs of up to 0.35.

Patient preference trial

We (conservatively) estimate that during the inclusion period a total of 180 patients (60% of the eligible patients) may decline to participate in the RCT, but are willing to take part in the preference observational study. Based on our clinical experience it is expected that 60% of these patients (n=108) prefers DBS, against 40% (n=72) preferring CLI.

When comparing the effect of DBS treatment of patients who express a preference for that treatment with the effect of DBS treatment in the randomised patients, and given the same test conditions (power, type-I error rate, two group t-test) we are able to detect a difference in

Version 7: 23-10-2019 17 of 48

mean PDQ-39 scores between both groups of 8,4, assuming an expected mean score of 32 in the randomized DBS group and a standard deviation of 15.

In case only 120 patients (40% of the eligible patients) agree to take part in the preference observational study, we are able to detect a difference in mean PDQ-39 scores between both DBS groups of 8,9.

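### The protocol's conversion gives a QALY SD of 0.30 to 0.375, so 0.35 is not its upper limit; power at 26 per group is about 75% at the top of the range, not 80%

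*Protocol*

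**What the plan says.** Protocol section 4.4 sizes the trial for the economic comparison. It takes "the difference in costs (i.e., €34,174 a year", divides by a willingness to pay of €120,000 per QALY, and concludes that "CLI treatment should at least outperform DBS treatment by 0.2847 QALY per year". It anticipates an SD of at most 0.35 for QALYs and at most €10,000 for total costs, and it assumes zero correlation between costs and effect. The result is stated as: "To achieve 80% power" and "given a two-sided significance level of 0.05", "up to 26 patients per group (or 52 in total) are needed". Allowing for 20% dropout, 33 per group are randomised.

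A short paragraph later in section 4.4 gives the reasoning for the QALY SD. It cites a PDQ-39 SD of 15 points in operated patients, says that "a 4 to 5 points difference is associated with a QALY difference of approximately 0.1", and ends with "suggesting a standard deviation for QALYs of up to 0.35". The SAP and the health economics analysis plan revise neither this SD nor the sample size.

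**The concern.** A figure introduced as a maximum should be the upper end of the range that produces it. The conversion is given as a range, and its 4-point end gives a larger SD than 0.35. Section 4.4 presents its inputs as limits (maximum SDs, a worst case for the correlation, a maximum number per group), so a reader will take 26 per group as sufficient over the whole stated range. At the 4-point end it is not. The 80% power claimed for the primary economic comparison is at stake, and an inconclusive result would be read against that figure.

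**Working it through.** **Inputs, all from protocol section 4.4**
- Two-sided α 0.05, target power 80%, two-sample t-test, n = 26 evaluable per group.
- Difference δ = 0.2847 QALY (34,174 / 120,000 = 0.2848; the protocol prints 0.2847).
- Cost SD €10,000, willingness to pay €120,000, correlation 0.
- PDQ-39 SD 15 points; 4 to 5 points per about 0.1 QALY.

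**Step 1. Reproduce the plan at QALY SD 0.35**
- With zero correlation, SD(NHB) = √(SD_QALY² + (SD_cost/WTP)²).
- SD_cost/WTP = 10,000 / 120,000 = 0.0833.
- SD(NHB) = √(0.35² + 0.0833²) = 0.3598.
- Normal approximation: n = 2 × (1.960 + 0.842)² × (0.3598/0.2847)² = 25.1, so 26 per group, as stated.
- Noncentral t, n = 26: noncentrality 0.2847 / (0.3598 × √(2/26)) = 2.85 on 50 degrees of freedom, power 79.9%. By this method strictly 27 per group are needed.
- Dropout: 26 / 0.8 = 32.5, so 33 per group, as stated.

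**Step 2. Apply the protocol's conversion**
- 5 points per 0.1 QALY: 15/5 × 0.1 = 0.300.
- 4.5 points: 15/4.5 × 0.1 = 0.333.
- 4 points: 15/4 × 0.1 = 0.375.
- Working back from 0.35: 15 × 0.1 / 0.35 = 4.29 points, a value that section 4.4 does not state.

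**Step 3. Power over that range (t-test, δ = 0.2847)**

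| QALY SD | SD(NHB) | Power, 26 per group | Power, 33 per group |
|---|---|---|---|
| 0.300 | 0.3114 | 89.9% | 95.5% |
| 0.333 | 0.3436 | 83.4% | 91.2% |
| 0.350 | 0.3598 | 79.9% | 88.6% |
| 0.375 | 0.3841 | 74.6% | 84.3% |

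**Step 4. Sensitivity at SD 0.375**
- On QALYs alone, with no cost variance, power at 26 per group is 76.6%. The normal approximation on the net-health-benefit scale gives 76.2%.
- For 80% power, 30 per group are needed by t-test (29 by normal approximation). After 20% dropout, 30 / 0.8 = 37.5, so 38 randomised per group against the planned 33.
- The largest QALY SD that keeps 80% power at 26 per group is about 0.350 by t-test (0.357 by normal approximation). At 26 evaluable there is almost no reserve above 0.35.

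**The case against.** The strongest reply is that the conversion is explicitly approximate and should not be pushed to its edge. The chosen 0.35 already exceeds the midpoint value of 0.333, so the calculation leans towards caution. Section 4.4 also attributes 0.35 to cited literature, with allowance for follow-up and non-responders, and that source cannot be checked from the documents. The 75% further requires the cost SD at its stated maximum and the full 20% dropout. Finally, nothing in the analysis depends on the planning SD: the health economics analysis plan reports bootstrap intervals and acceptability curves over a range of willingness-to-pay values.

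Most of this stands, and it limits the weight of the point. It does not rescue the sentence. The paragraph written to motivate the SD does not yield 0.35 as a maximum, whatever other support 0.35 may have. Nor can 33 evaluable per group be relied on. The protocol itself plans for 20% dropout, and the SAP (Synopsis of study protocol development) reports that several patients refused CLI straight after allocation; the economic analyses use the modified intention-to-treat population, which leaves them out.

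A reader might go further and infer that the cost difference is also wrong, and that both inputs make the power look too good. Protocol section 1 reports a "mean cumulative 5-year cost per patient (including the surgery) was estimated € 88,014 for DBS and € 233,986 for CLI", and (233,986 − 88,014) / 5 = €29,194 a year, below the €34,174 used. The documents do not support that inference. The lower figure is a five-year average from a Spanish study. The trial asks about societal costs in the Netherlands over one year, and nothing shows that the Spanish total covers the same components. Spreading the initial placement costs over five years, as section 12.5 plans, does not make that average the planning input. The protocol's own estimates for equipment and consumables in section 1 differ by 45,000 − 10,000 = €35,000, and €34,174 is about 2% below that. At €35,000 the power at SD 0.35 would be 81.8%, slightly above the stated 80%. What remains is that no derivation of €34,174 is shown, which is a reporting gap and not an error.

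**Conclusion.** The point holds, and it is minor. On the protocol's own inputs the QALY SD runs from 0.30 to 0.375, so 0.35 is a value within the range and not its limit. With 26 evaluable per group, power is about 80% at 0.35 and about 75% at 0.375, a loss of about 5 percentage points at one end of an approximate range. Over the rest of the range, down to 0.30, power is about 80% or higher.

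The 75% rests on a difference of 0.2847 QALY, willingness to pay of €120,000, cost SD of €10,000, zero correlation and a two-sided t-test at 0.05. It would not be right to conclude that the trial is materially underpowered or that 0.35 is an unreasonable planning value. Only its description as the upper limit is wrong, together with the impression that 26 per group gives 80% power across the whole range.

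**What to change.** In the paragraph of section 4.4 that motivates the QALY SD, replace the stated maximum with a range of 0.30 to 0.375. Add that 26 evaluable patients per group give about 80% power at SD 0.35 and about 75% at 0.375. If 0.35 is kept as the planning value, describe it as a choice within that range and give the reason. Carry the same change to the earlier sentence in section 4.4 that gives 0.35 as the maximum anticipated SD. One further sentence showing how €34,174 was obtained would close the reporting gap.

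The cost is one paragraph and a slightly less favourable statement of power. No more patients are needed, and no endpoint, analysis population or test changes.

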When comparing the effect of CLI treatment for patients who express a preference for that treatment with the effect of CLI treatment in the randomised patients, and given the same test conditions (power, type-I error rate, chosen test) we are able to detect a difference in mean PDQ-39 scores between both groups of 8,9, assuming an expected mean score of 43,9 in the randomized CLI group and a standard deviation of 15. In case only 120 patients (40% of the eligible patients) agree to take part in the preference observational study, we are able to detect a difference in mean PDQ-39 scores between both CLI groups of 9,6.

Version 7: 23-10-2019 18 of 48

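### The detectable PDQ-39 differences for randomised versus preference patients assume no dropout; with the protocol's own 20% loss in the randomised arms, their power is about 72–74%, not 80%

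*Protocol*

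**What the plan says.** All the figures are in Protocol section 4.4.

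- **Base calculation (RCT):** "To achieve 80% power and given a two-sided significance level of 0.05, up to 26 patients per group (or 52 in total) are needed".
- **Dropout (RCT):** "Accounting for a possible dropout of 20%, we will randomize 66 patients (33 per group").
- **PDQ-39 in the RCT:** the conditions read "given the same test conditions (power, type-I error rate, test chosen, drop-out rate"), so dropout is named as one of them. The result reads "difference in mean PDQ-39 scores between both groups of 11.9, assuming an expected mean score of 32 in the DBS group and a standard deviation"; the SD used is 15.
- **Preference cohort:** 180 patients are expected, and "it is expected that 60% of these patients (n=108) prefers DBS, against 40% (n=72) preferring CLI". A second scenario has 120 patients, with no split stated.
- **Randomised versus preference, DBS:** with 180 preference patients the text gives "mean PDQ-39 scores between both groups of 8,4, assuming an expected mean score of 32 in the randomized DBS group". The SD is 15. With 120 preference patients the figure is 8.9.
- **Randomised versus preference, CLI:** 8.9 with 180 preference patients. With 120 it is a "difference in mean PDQ-39 scores between both CLI groups of 9,6". The SD is again 15.

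The preference paragraphs call the conditions the same but list only power, type-I error rate and test; the DBS paragraph has "given the same test conditions (power, type-I error rate, two group t-test) we are able to detect a difference in". They give no dropout rate for either group and do not say that follow-up is taken as complete.

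**The concern.** The same randomised arms, with the same outcome and SD, appear to have 26 evaluable patients for the RCT figure and 33 for the preference comparisons a few lines later. Both cannot describe one trial under one dropout assumption. Someone coming from the RCT paragraph would reasonably take dropout to be included in all the figures.

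The preference arms are there to judge the external validity of the RCT. If the trial finds no clear difference between randomised and preference patients, that will be read as support for generalising the randomised result. How much support it gives depends on the difference the comparison could have seen, so overstating that sensitivity makes the reading too comfortable.

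**Working it through.** **Inputs (Protocol 4.4).** SD 15; two-sided alpha 0.05; power 80%; two-group t-test; 33 randomised per arm; 26 per arm after dropout (33 × 0.8 = 26.4, and the protocol's own requirement is 26); preference arms of 108 DBS and 72 CLI when the total is 180.

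**Assumption.** For a total of 120 the split is taken as the same 60/40, so 72 DBS and 48 CLI. The stated figures reproduce under it.

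**Formula.** SE = 15 × √(1/n₁ + 1/n₂), df = n₁ + n₂ − 2, noncentrality λ = d / SE. Power = 1 − F(t₀.₉₇₅,df ; df, λ), where F is the noncentral t distribution function. The detectable difference is the d that gives power 0.80.

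**Step 1: the RCT figure.**
- 26 v 26: SE = 15 × √(2/26) = 4.16; detectable difference 11.89, which matches 11.9.
- 33 v 33: SE = 15 × √(2/33) = 3.69; detectable difference 10.50, which does not match.

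The RCT figure therefore includes the dropout.

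**Step 2: the preference figures as stated.**

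| Comparison | Stated | 33 randomised, full preference arm | 26 randomised, full preference arm |
|---|---|---|---|
| DBS, 180 | 8.4 | 33 v 108: 8.42 | 26 v 108: 9.25 |
| DBS, 120 | 8.9 | 33 v 72: 8.92 | 26 v 72: 9.71 |
| CLI, 180 | 8.9 | 33 v 72: 8.92 | 26 v 72: 9.71 |
| CLI, 120 | 9.6 | 33 v 48: 9.62 | 26 v 48: 10.37 |

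Only the 33-patient column matches. Keeping 33 randomised but removing 20% of the preference arms (86, 58, 38) gives 8.68, 9.26 and 10.14, which does not match either. The stated figures therefore contain no dropout in either group.

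Hand check of the first row with the normal approximation: 15 × (1.960 + 0.842) × √(1/33 + 1/108) = 8.36. With 26 in place of 33 it is 9.18. The gap is the same as with the t distribution.

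**Step 3: power at the stated differences.**

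| Comparison (difference) | No loss | 20% loss, randomised arm only | 20% loss, both groups |
|---|---|---|---|
| DBS, 180 (8.4) | 79.8% | 72.1% (26 v 108) | 69.9% (26 v 86) |
| DBS, 120 (8.9) | 79.8% | 72.8% (26 v 72) | 70.0% (26 v 58) |
| CLI, 180 (8.9) | 79.8% | 72.8% (26 v 72) | 70.0% (26 v 58) |
| CLI, 120 (9.6) | 79.8% | 73.7% (26 v 48) | 69.7% (26 v 38) |

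The 79.8% rather than 80% reflects only the rounding of the stated differences. The normal approximation gives 73–75% and 71% in the last two columns.

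**Step 4: differences detectable at 80% power, in the same row order.**
- Loss in the randomised arm only: 9.2, 9.7, 9.7, 10.4.
- Loss in both groups: 9.5, 10.0, 10.0, 10.9.

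**The case against.** Each stated figure is correct for its inputs, and dropout is left out of the list of conditions in the preference paragraphs. So this could be called an unstated assumption rather than a miscalculation. That is fair as a description of the fault, but omitting an item from a list headed as the same conditions does not tell anyone that complete follow-up was assumed.

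A reader might infer that power is simply about 70%. The documents do not support that as the main figure. The 20% is tied to the 66 randomised patients, and no loss rate is given for the preference arms. Preference patients have telephone assessments only (Protocol 7.3) and about 5 hours of study burden against about 15 (Protocol 9.3), so borrowing the RCT rate is open to question. On the other side, the 180 and 120 are counts of people willing to take part, and the SAP analyses only those who started treatment and had a baseline and at least one follow-up visit, so some loss is likely. The 70% belongs in the text as the lower end of a range.

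The 120-patient scenario covers some preference-arm shortfall, since 20% off 180 leaves 144. It does nothing for the fall from 33 to 26 in the randomised arms.

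The objection that little depends on these figures largely stands. The SAP sets no minimum for the preference arms and reports these contrasts as differences with 95% confidence intervals, without P-values. It analyses change from baseline, while section 4.4 works with mean scores. It imputes missing PDQ-39 values, so the number analysed is not simply 26, although imputation does not restore all the lost information. It also cites a minimal important difference of 1.6 points; 8.4 and 9.2 are both more than five times that (8.4/1.6 = 5.3; 9.2/1.6 = 5.8).

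**Conclusion.** The point holds for the loss that the protocol itself plans. The stated preference-comparison differences assume 33 evaluable randomised patients per arm, whereas the section's own dropout leaves 26. Power at those differences is then about 72–74%, so the chance of missing a true difference of that size is about 26–28%, not 20%. At 80% power the detectable differences are about 0.8 points larger than stated (for example 9.25 − 8.42 = 0.83 for DBS with 180 patients).

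This rests on SD 15, the t-test on mean scores as in section 4.4, and a 60/40 split of the 120. The figure of about 70% needs the further assumption of 20% loss in the preference arms.

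Nor should a reader conclude that the trial's sample size is wrong. The 66 patients rest on the QALY calculation, and the RCT PDQ-39 figure already includes dropout. This is a correction to stated figures for a secondary comparison, worth making because it is cheap.

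**What to change.** Change the text of Protocol section 4.4, or correct the figures wherever they are next reported, in one of two ways.

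1. Restate the differences detectable at 80% power with 26 randomised patients per arm: about 9.2 (DBS, 180 preference patients), 9.7 (DBS, 120), 9.7 (CLI, 180) and 10.4 (CLI, 120). Add 9.5, 10.0, 10.0 and 10.9 as the range if 20% loss is also assumed in the preference arms, labelled as an added assumption.
2. Keep 8.4, 8.9, 8.9 and 9.6, say that they assume complete follow-up, and give the power under the planned loss as about 72–74% (about 70% with 20% loss in both groups).

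In either case, state the 60/40 split used for the 120-patient scenario. The only cost is that the figures look slightly less favourable; sample size, data collection and planned analyses stay as they are.

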5. TREATMENT OF SUBJECTS

5.1 Investigational product/treatment

CLI and DBS are both complex treatments and are therefore performed by teams that consist of various specialties (e.g. neurologist, neurosurgeon, gastroenterologist, and specialized nurses). In the Netherlands, 6 centres are permitted to perform DBS. Three of these also offer CLI, but in a much smaller number. CLI is performed in approximately 45 centres. For the study, CLI and DBS treatments should be optimally performed, i.e. by the best-trained teams. It is inevitable that the centres that perform the treatments at present perform the study-treatments as well. This implies that CLI and DBS will be carried-out in different centres. An advantage of this (Dutch) situation is that the study design closely resembles the current clinical practice, and as such the study results will be highly externally valid.

DBS treatment (Medtronic, Minneapolis, MN, USA)

Treatment is in accordance with the usual care regarding this procedure. For DBS, a neurosurgeon places two electrodes in the brain. These are connected to an implantable pulse generator. Patients are on average 4 days hospitalized. Patients do not receive PD drugs on the day of surgery until the end of the procedure. A stereotactic technique will be employed for implantation with the Leksell stereotactic frame (Elekta, Stockholm, Sweden) and guided by MRI. For this part of the surgery, patients will have local or general anaesthesia, both methods are possible in usual care and the surgeon will decide the method with the patient. The decision for electrode placement is based on MRI, microelectrode recordings and macro-electrode stimulation effects. A four contact electrode will be implanted in the subthalamic nucleus (STN). Subsequently, patients will have a second surgery under general anaesthesia to implant the pulse generator (ActivaPC or ActivaSC), subcutaneously in the subclavian area. The electrodes are connected to the pulse generator. During the course of the study, changes in drug treatment are allowed. Patients will regularly visit the outpatient clinic to adjust stimulation parameters and PD medication while assessing the interaction between both treatments.

CLI treatment (Duodopa, Abbott, Abbott Park, IL, USA)

Treatment is in accordance with the usual care regarding this procedure. In CLI, a levodopa-gel is continuously administered through a tube in the jejunum. The CLI-gel is dispensed into cassettes connected to an ambulatory programmable pump that delivers the suspension. One cassette supplies 100 ml gel containing 2000 mg levodopa and 500 mg carbidopa that lasts — depending on the individual needs — on an average 16 hours.

Version 7: 23-10-2019 19 of 48

The pump and cassette weight approximately 0.5 kg. The initiation and dose adjustments of CLI require 5 to 12 days of hospitalization. In some centres, a temporary nasoduodenal tube is used to find out if the patient responds favourably to continuous levodopa infusion on day 1 to 3. On day 1 or 4 (depending on whether a temporary nasoduodenal tube is used first), a gastroenterologist endoscopically places a PEG tube in the stomach with an extension tube clipped in the jejunum using local anaesthetic and sedation with a short acting benzodiazepine. The tube is subsequently connected to the pump. Thereafter, CLI will immediately be continued and subsequently adjusted within the following days of inpatient stay. On day 5 to 12, the patient will be discharged. Patients will regularly visit the outpatient clinic to adjust the dose. Most patients use the pump only during daytime.

